Preliminary data: We completed a randomized, double blind, placebo-controlled pilot clinical trial at the Lurie Center/MassGeneral Hospital for Children from 01/2011 to 12/2013 (clinical trials identifier NCT01474993)²⁴ to test the efficacy of sulforaphane in 44 male adolescents and adults (13-30 years) with ASD. Fifteen participants were randomized to placebo and 29 to sulforaphane. Forty participants (14 on placebo and 26 on sulforaphane) completed the trial; of those 32 (80%) had a history of positive behavioral responses to fever. All participants were treated for 18 weeks with study visits at baseline, 4, 10 and 18 weeks, followed by a final visit at 22 weeks, 4 weeks after treatment ended. Parent/caregivers completed the Aberrant Behavior Checklist (ABC)²⁵ and Social Responsiveness Scale (SRS)²⁶ and study physicians completed the Ohio Autism Clinical Impressions Severity and Improvement Scales (OACIS-S and OACIS-I)^{27,28} to document severity of autistic behavior at each visit. OACIS-S and -I evaluate severity and improvement of ASD symptoms in the following subdomains: general level of autism, social interaction, aberrant/abnormal behavior, stereotypical behavior, verbal communication, non-verbal communication, hyperactivity and inattention, anxiety/fears, sensory sensitivities and restricted interests. Participants were monitored with regular physical examinations and clinical laboratory studies.

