
Pharmacy at dose specific for child, dispense but hold before starting until review of clinical lab studies, then call to start medication.
 
7-week visit: Review progress; Perform CGI-I; ABC and SRS by parents; physical exam; phlebotomy/urine for clinical and research lab studies. Dispense BSP.
 
15-week visit: Review progress; Perform CGI-I; ABC and SRS by parents; physical exam; phlebotomy/urine for clinical and research lab studies. Dispense BSP.
 
22-week visit: Review progress; Perform CGI-I; ABC and SRS by parents; physical exam; phlebotomy/urine for clinical and research lab studies. Dispense BSP.
 
30-week visit: Review progress; Perform CGI-I; ABC and SRS by parents; physical exam; phlebotomy/urine for clinical and research lab studies. Discontinue medication
 
36-week visit: Review progress; Perform CGI-I; ABC and SRS by parents; physical exam; phlebotomy/urine for research lab studies. Record exit comments on study.
		
Task 5: Data storage and analysis	0-36 mo.	
SPECIFIC AIM 3: To elucidate cellular biomarkers that support the hypothesized mechanism of action of sulforaphane in ASD. Blood and urine samples will be collected at UMass in Pilot and Main clinical trial, processed, stored and shipped on dry ice to JH		
Task 1: Labwork at JH for Pilot Study of biomarkers: Nrf2, oxidative stress markers, heat shock proteins, mitochondrial functions, mTOR, cytokine	3-6 mo.	3-6 mo.
Task 2: Labwork at JH for Main Clinical Trial : biomarkers and mechanisms	6-36 mo.	6-36 mo.

ANTICIPATED TARGET ENROLLMENT (QUARTERLY):

	Year 1				Year 2				Year 3				TOTAL
	Q1	Q2	Q3	Q4	Q1	Q2	Q3	Q4	Q1	Q2	Q3	Q4	
Target Enrollment Pilot Study	10	-	-	-	-	-	-	-	-	-	-	-	10
Target Enrollment Main Study (per quarter) (does not include the pilot study participants, who will not take part in the main study because they will no longer be sulforaphane naïve)	-	7	10	8	8	5	3	3	2	2	2	0	50

9) Study Endpoints*

a) *Primary study endpoint:*

- i) Ohio Autism Clinical Impressions Scale – Improvement (OACIS-I) Average Score.
- b) *Secondary study endpoints:*
- i) OACIS-I response rate (much or very much improved) on aberrant behaviors
 - ii) OACIS-I response rate (much or very much improved) on social communication
 - iii) Change in total ABC score (as well as subscales of Irritability, lethargy and social withdrawal, stereotypic behavior, hyperactivity and inappropriate language) from baseline

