 - iv) Change in total SRS score (as well as subscales of social awareness, social cognition, social communication, social motivation and autistic mannerisms) from baseline
 - v) Determination of Nrf2 levels
 - vi) Determination of oxidative stress biomarkers
 - vii) Determination of Heat Shock Response biomarkers
 - viii) Determination of mitochondrial function biomarkers
 - ix) Determination of mTOR signaling pathway markers
 - x) Determination of immune function and inflammatory biomarkers
- c) *Safety endpoints*
- i) Liver function tests (ALT/AST)
 - ii) Renal function tests (serum creatinine)
 - iii) Thyroid function (TSH levels)
 - iv) Complete blood counts (WBC count, RBC count, platelet counts)
 - v) Urinalysis

Description of surveys used as the primary and secondary study endpoints:

1. **Ohio Autism Clinical Impressions Scale - Severity (OACIS-S)**^{27,28} is a 7 point, 10 domain scale that requires the clinician to rate the severity of the patient's ASD at the time of assessment, relative to the clinician's past experience with patients who have the same diagnosis. The questions are rated on a scale from 1 to 7 in the increasing order of severity, where “1” is normal (symptoms indistinguishable from typically developing children) and “7” is the most severe symptoms causing significant problems with individual functioning on a daily basis. The 10 items on the OACIS-S scale cover different domains of patients’ behavior, including global autism severity, social interaction, aberrant behavior, repetitive or ritualistic behaviors, verbal communication, non-verbal communication, hyperactivity/inattention, anxiety, sensory sensitivities and restricted/narrow interests. These are rated in a similar way to the NIMH CGI Severity scale, but it

- is focused on autism spectrum symptoms. This scale will be used to acquire clinician-assessed severity of autistic symptomatology in the study.

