A secondary analysis assessing proportion of participants in both groups who have responded to the study drug will be performed by Fisher's Exact test. This analysis will be done by categorizing the OACIS-I, SRS and ABC data. Participants will be considered as responders to study drug if they experience either of the following: they are much/very much improved (a score of 2 or less) on any subdomain of OACIS-I scale, their total ABC scores at 15 weeks decrease by at least 25% from baseline score, and their total SRS scores at 15 weeks decrease by at least 25% from their baseline score.

Biomarkers (testing mechanism of action of SFN) will be tested both as outcome variables in mixed model analyses and as predictors of differences in behavioral symptoms using the models described above for behavioral symptoms. Markers that both respond to sulforaphane treatment and predict differences in behavioral symptoms will be interpreted as possible mediators of any benefit from sulforaphane treatment. Safety of sulforaphane treatment will be assessed based on absolute rates of liver, thyroid and renal toxicity among participants treated with sulforaphane and based on comparison of the proportion of participants with such toxicities between the two treatment groups.

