Power Calculations: We plan to enroll a total of 50 participants in the study, randomized 1:1 to sulforaphane and placebo. With OACIS-I, ABC, and SRS assessments at 0, 7 and 15 weeks our proposed design will have at least 80% power to detect significance in the following outcome measures if the following sample sizes are considered: **OACIS-I average Score:** With a total of 40 patients (20 on placebo and 20 on sulforaphane) entering this two-treatment parallel-design study, the probability is 80 percent that the study will detect a treatment difference at a two-sided 0.05 significance level, if the true difference of average OACIS-I score at 15 weeks between two treatments is 4 units. This is based on the assumption that the standard deviation of the average OACIS-I score is 4.9. **OACIS-I response rate on aberrant behaviors:** With a total of 44 patients (22 on placebo and 22 on sulforaphane) entering this two-treatment parallel-design study, there will be an 88% chance of detecting a significant difference at a two sided 0.05 significance level. This assumes that the response rate at 15 weeks of placebo is 9% and the response rate of sulforaphane is 54% on aberrant behavior subscale of OACIS-I. **OACIS-I response rate on social communication:** With a total of 44 patients (22 on placebo and 22 on sulforaphane) entering this two-treatment parallel-design study, there will be 82% chance of detecting a significant difference at a two sided 0.05 significance level. This assumes that the response rate of placebo is 7% and the response rate at 15 weeks of sulforaphane is 46% on the social communication subscale of OACIS-I. **Change in total ABC score from baseline:** With a total of 44 patients (22 on placebo and 22 on sulforaphane) entering this two-treatment parallel-design study, the probability is 81 percent that the study will detect a treatment difference at a two-sided 0.05 significance level, if the true difference of change in baseline of total ABC score at 15 weeks between the two treatments is 19.4 units. This is based on the assumption that the standard deviation of the change in ABC score is 22.1. **Change in total SRS score from baseline:** With a total of 48 patients (22 on placebo and 22 on sulforaphane) entering this two-treatment parallel-design study, the probability is 81 percent that the study will detect a treatment difference at a two-sided 0.05 significance level, if the true difference of change from baseline of total SRS score at 15 weeks between two treatments is 18.4 units. This is based on the assumption that the standard deviation of the change in SRS score is 22.0. Thus our proposed sample size of 50 participants, randomized 1:1 to sulforaphane and placebo will have more than enough power to detect significantly changes in majority of the outcomes listed above. The study will have 80% power to detect one or more toxicities expected to occur in at least 5.3% of sulforaphane-treated participants. The study is not powered to compare rates of safety outcome between sulforaphane and placebo treatment groups for a relevant non-inferiority threshold.

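### The only efficacy responder rule (improvement on any OACIS-I subdomain) is not the single-domain response endpoint that was listed and powered, and one listed endpoint names a domain OACIS-I does not have

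*Combined protocol and SAP*

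**What the plan says.** All references are to the combined protocol and SAP.

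**Endpoints (section 9).** The first two secondary endpoints are "OACIS-I response rate (much or very much improved) on aberrant behaviors" and "OACIS-I response rate (much or very much improved) on social communication".

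**Power Calculations (section 12).** Each endpoint is sized on its own at 22 per arm, two-sided 0.05. One assumes that "the response rate at 15 weeks of placebo is 9% and the response rate of sulforaphane is 54% on aberrant behavior subscale", with power 88%. The other assumes that "the response rate of placebo is 7% and the response rate at 15 weeks of sulforaphane is 46% on the social communication subscale", with power 82%.

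**Statistical Analysis (section 12).** One secondary responder analysis is assigned to Fisher's exact test. It begins "Participants will be considered as responders to study drug if they experience either of the following" and gives three criteria. The OACIS-I criterion is "they are much/very much improved (a score of 2 or less) on any subdomain of OACIS-I scale". The other two are falls of at least 25% from baseline in total ABC and total SRS at week 15, the last joined by *and*. Neither listed OACIS-I domain is named.

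**Domains.** Section 4 lists the OACIS subdomains as "general level of autism, social interaction, aberrant/abnormal behavior, stereotypical behavior, verbal communication, non-verbal communication, hyperactivity and inattention", followed by anxiety, sensory and restricted-interest items. Section 9 lists "global autism severity, social interaction, aberrant behavior, repetitive or ritualistic behaviors, verbal communication, non-verbal communication", followed by hyperactivity/inattention, anxiety, sensory sensitivities and restricted interests, and says OACIS-I uses the same ten domains. Social communication appears in section 9 as an SRS subscale.

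**A per-domain sentence.** The OACIS-I description in section 9 also mentions comparing, between arms, the proportion improved on each of the ten domains. It is in the past tense, names no test and no visit, and omits the word *much* from its lower response category.

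**The concern.** An analyst following the Statistical Analysis text would test a different quantity from the one listed and powered. A child rated 2 on, say, sensory sensitivities alone is a responder under the any-subdomain rule but under neither listed endpoint. The 88% and 82% could then be quoted for an analysis they do not describe.

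The list can also be read as an any-criterion composite or as three separate per-scale analyses, and these give quite different response rates. If the reading is not fixed before unblinding, it can be chosen after the data are seen.

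Finally, one of the two listed response endpoints names a domain that the OACIS-I form does not contain. Someone will have to decide which item to use, and the plan does not say who decides or when.

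**Working it through.** **1. Reproduce the stated powers.** Inputs (section 12, Power Calculations): n = 22 per arm, two-sided α = 0.05, and the two pairs of rates. Method: power = Σ over x, y of Bin(x; 22, p₀)·Bin(y; 22, p₁), summed over all 2×2 tables with two-sided Fisher p ≤ 0.05.

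| Rates | Stated | Fisher, 22/arm | Pooled normal, 22/arm | Fisher, 25/arm |
|---|---|---|---|---|
| 9% vs 54% | 88% | 88.1% | 92.4% | 91.7% |
| 7% vs 46% | 82% | 81.3% | 86.0% | 85.4% |

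Fisher's test on single domains reproduces the plan; the normal approximation does not. With 12/26 in place of the rounded 46%, the second figure is 81.5%, which rounds to the stated 82%. So Fisher on the two named domains was probably intended.

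**2. Can those powers be used for the any-subdomain rule?** That needs any-subdomain rates in both arms. Section 4 gives 17 of 26 sulforaphane completers in the earlier trial. Counting the 29 − 26 = 3 dropouts as non-responders gives 17/29 = 58.6%. No placebo any-subdomain rate is reported. Aberrant behavior alone gives at least 1/15 = 6.7%, and six of the ten domains are not reported. The placebo rate must therefore be assumed. Exact Fisher power at 25 per arm:

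| Assumed placebo rate | vs 17/29 | vs 17/26 |
|---|---|---|
| 10% | 95% | 99% |
| 20% | 76% | 89% |
| 30% | 46% | 66% |

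The range shows only that the power is undetermined.

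**3. How far apart are the readings of the list?** Earlier-trial figures (section 4), dropouts as non-responders:

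- *Any criterion:* sulforaphane at least 17/29 = 59%; placebo at least 2/15 = 13%, from ABC alone.
- *Separate tests:* ABC 15/29 = 52% vs 2/15 = 13%; SRS 9/29 = 31% vs 0%; OACIS-I on its own.
- *All three:* sulforaphane at most 9/29 = 31%; placebo 0%. This is the least natural reading of a sentence that begins with *either*.

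**4. Which domain is meant by social communication?** Section 4 reports earlier-trial sulforaphane responders over 29 randomized; 26 completed. Assuming all responders were completers:

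- social interaction: 12/26 = 46.2%, matching the assumed 46%
- verbal communication: 11/26 = 42.3%, no match
- aberrant behavior: 14/26 = 53.8%, matching the assumed 54% for the other endpoint

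The placebo assumptions do not help. Among 14 placebo completers, aberrant behavior is 1/14 = 7.1% and social interaction is 0%, whereas the plan attaches 9% to aberrant behaviors and 7% to social communication. Planning rates need not equal earlier-trial rates, so this neither confirms nor excludes social interaction.

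**The case against.** The best defence combines two places. Section 9 says proportions are compared on each of the ten OACIS-I domains, and section 12 assigns responder proportions from categorized OACIS-I data to Fisher's test with a cut-off of 2. Read together, a single-domain Fisher comparison has a source, and the Power Calculations supply week 15. The social communication label looks like a slip for social interaction. The responder analysis is explicitly secondary.

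Much of this stands. Single-domain analysis is not wholly absent, and week 15 is the likely visit. But the section 9 sentence does not single out the two listed endpoints, and its looser wording could admit a rating of 3 (minimally improved). The section 12 rule says *any subdomain*. A reader has to override one passage with another to reach the intended analysis.

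Four stronger readings are tempting and are not supported:

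- *The stated powers are wrong.* They reproduce for the endpoints they name.
- *The any-subdomain analysis is underpowered.* The documents give no placebo rate from which to say so; at 10% its power would be high.
- *The second endpoint can never be scored.* The 12/26 match suggests a wrong label that the sponsor can correct.
- *The main efficacy conclusion is at risk.* The primary endpoint, the OACIS-I average score, does not use this rule.

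**Conclusion.** The point holds as a mismatch in the secondary analyses that should be corrected. The plan lists and powers two single-domain OACIS-I response endpoints, but its one efficacy responder rule tests improvement on any subdomain, states no OACIS-I visit, and does not say whether the three criteria form a composite or separate tests. The 88% and 82% belong to the named endpoints only. The any-subdomain rule has no determinable power; the 95% to 46% range rests on assumed placebo rates of 10% to 30% and on the earlier adolescent and adult trial's 17/29 recurring in children.

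Social communication is not an OACIS-I domain. Social interaction is the likely intended one, an inference from a single matching fraction that assumes all earlier responders were completers. Confidence in the textual mismatch is high; the choice of domain is for the sponsor to confirm.

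**What to change.** 1. In section 12, Statistical Analysis, define OACIS-I response as a week-15 score of 2 or less on (a) aberrant behavior and (b) the existing OACIS-I domain that the sponsor confirms, each compared between arms by a two-sided Fisher's exact test.
2. Correct the domain name in section 9 and in the Power Calculations, and confirm that 7% vs 46% belongs to that domain.
3. Align the threshold in the section 9 OACIS-I description with the score-of-2 cut-off.
4. Replace the *either ... and* list with one stated reading, fixed before unblinding. Separate 25% ABC and 25% SRS response tests would match how section 4 reports the earlier trial, but the choice is the sponsor's.
5. Label any any-subdomain or composite responder rate as an additional analysis not covered by the stated power.

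The cost is wording only; no patients or data are added. The downside is that the any-subdomain rate can no longer borrow the 88% and 82%. If separate ABC and SRS tests are chosen and the earlier rates recur, exact Fisher power at 25 per arm is about 77% for ABC (2/15 vs 15/29) and 84% for SRS (0 vs 9/29).

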2. **Ohio Autism Clinical Impressions Scale – Improvement (OACIS-I)^{27,28}** is a 7 point, 10 domain scale that requires the clinician to assess how much the patient's ASD has improved or worsened relative to a baseline state at the beginning of the intervention and rated as: “1”, very much improved; “2”, much improved; “3”, minimally improved; “4”, no change; “5”, minimally worse; “6”, much worse; or “7”, very much worse. The 10 domains in which improvement is assessed are the same as those used in the OACIS-S scale. For this study, the proportion of patients who were rated as improved or very much improved on each of 10 domains of OACIS-I were compared between sulforaphane and placebo groups. This scale will be used to gauge the clinician assessment of improvement in autistic symptomatology at all follow up visits as compared to the previous study visits.
 3. **Social Responsiveness Scale (SRS)²⁶**: SRS is a parent- and/or teacher-reported 65 point scale covering 5 treatment subscales focusing on the social communication domain of ASD as observed in natural (non-clinical) settings. Each item on the scale inquires about an observed aspect of reciprocal social behavior that is rated on the questionnaire on a scale from “1” (never true), “2” (sometimes true), “3” (often true), and “4” (almost always true). Its quasi-interval, ordinal design facilitates assessing degrees of change and/or severity of symptoms in response to an intervention. The SRS scale scores is subdivided into 5 subscales (social awareness, social cognition, social communication, social motivation and autistic mannerisms). This scale will be used at all study visits and the scores (as well as change thereof from the baseline visit) will be used as one of the clinical outcome measures assessing social interaction skills in the study.

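### The primary-endpoint power statement does not follow from its own inputs (71% at 20 per arm, not 80%), and its SD of 4.9 is impossible for an average of items rated 1 to 7

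*Combined protocol and SAP*

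**What the plan says.** Section 9 names the primary endpoint as the OACIS scale's "Improvement (OACIS-I) Average Score". The survey description in the same section calls OACIS-I a "7 point, 10 domain scale that requires the clinician to assess how much" the child has changed, with ratings from 1 (very much improved) through 4 (no change) to 7 (very much worse). How the ten ratings become one score is not stated.

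Section 12 (Power Calculations) plans 50 children randomized 1:1. Its line for the primary endpoint reads:

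- sample size: "With a total of 40 patients (20 on placebo and 20 on sulforaphane) entering this two-treatment parallel-design study"
- power and test: "the probability is 80 percent that the study will detect a treatment difference at a two-sided 0.05 significance level"
- effect: "if the true difference of average OACIS-I score at 15 weeks between two treatments is 4 units"
- variability: "the standard deviation of the average OACIS-I score is 4.9"

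The SRS line opens "With a total of 48 patients (22 on placebo and 22 on sulforaphane) entering this two-treatment parallel-design study" and claims 81% power. The section concludes that 50 children "will have more than enough power to detect significantly changes in majority of the outcomes listed above". It gives no source for the 4 or the 4.9, and no allowance for dropout.

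**The concern.** This line is the sample-size basis for the primary endpoint, and it has two faults. The power does not follow from the inputs. The inputs also do not suit the score they are attached to: 4.9 is too large an SD for an average on a 1-to-7 scale, and 4 units is more than a child can improve from no change (4 down to 1 is 3 units).

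Read at face value, the trial needs 40 children and enrols 50, which leaves 10 to absorb losses. If 80% in fact needs 48 to 50, that reserve is largely or wholly gone. A reader also cannot tell whether the target effect is 4 points on a total or on an average, so cannot judge whether it is realistic.

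**Working it through.** **Inputs** (Section 12, Power Calculations): difference 4, SD 4.9, 20 per arm, two-sided alpha 0.05, stated power 80%. Comparison lines: ABC, difference 19.4, SD 22.1, 22 per arm, stated 81%; SRS, difference 18.4, SD 22.0, total 48 but 22 + 22 listed, stated 81%; response rates of 9% vs 54% (stated 88%) and 7% vs 46% (stated 82%), 22 per arm.

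**Step 1. The primary line.** The standardized difference is d = 4/4.9 = 0.816. For n per arm the noncentrality is d × √(n/2); at n = 20 it is 0.816 × √10 = 2.58.

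- Normal approximation: Φ(2.58 − 1.96) = 73.3%.
- Two-sample noncentral t on 38 degrees of freedom: 71.1%.

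Neither gives 80%.

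**Step 2. Is the method right?** Applying standard methods to the other lines:

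| Outcome | n per arm | Method | Recomputed | Stated |
|---|---|---|---|---|
| ABC change | 22 | t-test | 81.2% | 81% |
| SRS change | 24 | t-test | 81.0% | 81% |
| SRS change | 22 | t-test | 77.3% | 81% |
| Aberrant behavior response | 22 | Fisher exact | 88.1% | 88% |
| Social communication response | 22 | Fisher exact | 81.3% | 82% |
| **OACIS-I average** | **20** | **t-test** | **71.1%** | **80%** |

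The SRS line is consistent only with 24 + 24 = 48, so its listed split is the slip. A one-sided test would give 81.3% for OACIS-I, but the text says two-sided, and one-sided testing would put ABC at 88.9%.

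**Step 3. What 80% requires.** By normal approximation n = 2 × (1.960 + 0.842)² × (4.9/4)² = 23.6, so 24 per arm (80.7%). By t-test n = 24.55, so 25 per arm (80.7%). With 25 + 24 the t-test gives 79.9%. The reserve is therefore 50 − 48 = 2 or 50 − 50 = 0 children.

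Holding 20 per arm, an SD of 4.40 or a difference of 4.45 would give 80%. A misprinted sample size (40 for 50) would also fit. The documents do not show which, if any, is the error.

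**Step 4. Can the score have an SD of 4.9?** A score bounded by 1 and 7 has SD at most (7 − 1)/2 = 3.0; the sample SD for 20 children is at most 3.0 × √(20/19) = 3.08. So 4.9 is impossible for an average. On a 10-to-70 sum the limit is (70 − 10)/2 = 30, and 4.9 is possible. Dividing by ten to return to an average gives 0.4/0.49, the same d, so the 71% stands on either scale.

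**Step 5. Sensitivity to loss.** Complete-case t-test power starting from 25 per arm. The loss rates are assumptions; 9% is the earlier sulforaphane trial's 4 of 44, in older males over 18 weeks.

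| Loss | n per arm | OACIS-I, SD 4.9 | OACIS-I, SD 4.4 |
|---|---|---|---|
| 0% | 25 | 81% | 88% |
| 5% | 23.75 | 79% | 87% |
| 9% | 22.73 | 77% | 85% |
| 15% | 21.25 | 74% | 82% |
| 20% | 20 | 71% | 80% |

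At 0%, 9% and 20% loss, SRS gives 83%, 79% and 73%, and ABC gives 86%, 82% and 77%.

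**The case against.** The strongest reply is that the design survives. At 25 + 25 with complete data the stated inputs give 80.7% for OACIS-I, 82.6% for SRS, 86.0% for ABC, and 91.7% and 85.4% for the two response rates. Every listed outcome reaches 80%, and the plan's conclusion claims adequacy only for most of them. This stands: the error does not show an underpowered trial. It does not rescue the printed line, which claims 80% at 20 per arm and implies a reserve that these inputs do not provide.

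A second reply is that average may mean the group mean of a 10-to-70 total. Section 4 uses the word that way for ABC, and the Statistical Analysis text speaks of total scores for OACIS-I, SRS and ABC together. That would make 4 and 4.9 possible values. But Section 9 names an average score as the endpoint, no section defines a sum, and power is 71% on either reading.

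Two narrower points are fair. The 3-unit limit on improvement from no change does not strictly rule out a 4-unit difference between arms, since placebo children could worsen; only the SD is excluded outright. The loss figures use assumed rates and complete cases, whereas the planned mixed model keeps week-7 data, so late dropout may cost less than shown.

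**Conclusion.** The concern holds. As printed, the primary-endpoint line overstates power by about 9 percentage points by t-test (71% against 80%), or about 7 by normal approximation (73%). An SD of 4.9 cannot belong to an average of ratings from 1 to 7. The SRS line contradicts itself: 24 + 24 supports its 81%, while 22 + 22 gives 77%.

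The consequence is a lost margin, not a failed design. If 4 and 4.9 stand, 50 children with complete data give about 81%, and 9% loss would bring complete-case power to about 77%. If the SD was meant to be 4.4, power at full enrolment would be 88%, and even 20% loss would leave 80%. The documents cannot settle which applies. Because this is the stated basis for the primary endpoint's sample size, it must be corrected.

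**What to change.** 1. Confirm the SD, the difference and the form of the OACIS-I score (average of ten domains or 10-to-70 total), and cite where the two numbers came from. Make Section 9, the Statistical Analysis text and the Power Calculations agree.
2. If 4 and 4.9 stand (or 0.4 and 0.49 for an average, if they came from a total), restate the line as 71% at 20 per arm and 81% at 25 per arm, and give power over a range of dropout. If an input was misprinted, correct it and recompute.
3. Correct the SRS split to 24 + 24.
4. Replace the concluding claim of ample power with the restated figures.

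The cost is a wording change to the combined protocol and SAP, once the sponsor has checked the source of two inputs. Enrolment, analysis and alpha stay as they are. The stated primary power may come out less favourable than the present text suggests.

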Results from clinical trial in young adult males with ASD: Sulforaphane was well tolerated and there were no significant toxic effects. SRS scores decreased by an average of -15 units in the sulforaphane group compared to -3 units in participants on placebo ($p=0.02$); considering the 4 drop-outs as non-responders, 31% (9/29) sulforaphane participants vs 0% placebo participants had a 25% decrease in total SRS score from baseline ($p=0.018$). The average change in total ABC score was -18 units in the sulforaphane group as compared to -1 units in the placebo group ($p=0.0001$), and after considering the 4 drop-outs as non-responders, 52% (15/29) sulforaphane participants vs. 13% (2/15) placebo participants had a 25% decrease in their total ABC score from the baseline ($p=0.02$). On the OACIS-I, participants on sulforaphane were much improved or very much improved on the following subdomains: social interaction, 41% (12/29) sulforaphane participants vs. 0% on placebo ($p=0.003$); aberrant/abnormal behavior, 48% (14/29) on sulforaphane vs. 6.7% (1/15) on placebo ($p=0.007$); repetitive/stereotypical behavior, 21% (6/29) on sulforaphane vs. 0% placebo ($p=0.08$); and verbal communication, 38% (11/29) on sulforaphane vs. 0% placebo ($p=0.008$). Seventeen of the 26 participants on sulforaphane who completed the trial were much or very much improved on at least one subdomain of the OACIS-I. Ninety-four percent (16) of those 17 on sulforaphane had a history of positive behavioral effects during febrile illness. In comparison, of the remaining 9 participants who were taking sulforaphane but were not much/very much improved on OACIS-I, only 55% (5/9) had a history of positive effects of febrile illness ($p=0.03$).

5) Inclusion and Exclusion Criteria*

- Inclusion criteria
 - Autism (ASD) diagnosis. Quantitative autism traits and severity for diagnosis of autism will be assessed by clinical judgment corroborated by the ADOS-G and DSM-V checklist of symptoms. ASD symptoms moderate to severe, based on ADOS criteria.
 - Age from 3 through 12 years.
- Exclusion criteria for subjects will include:
 - Absence of a parent or legal guardian and consent
 - Inability to speak/understand English language

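### The SRS power line states 48 patients but arms of 22 + 22 = 44; the printed arms give 77% power, and the stated 81% matches 24 per arm

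*Combined protocol and SAP*

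**What the plan says.** Section 12 (Data Management), under Power Calculations, opens with the enrolment: "We plan to enroll a total of 50 participants in the study, randomized 1:1 to sulforaphane and placebo". It then promises at least 80% power for each listed outcome at the sample size given for that outcome.

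For SRS the sample size is "With a total of 48 patients (22 on placebo and 22 on sulforaphane". The power claim for that size is "the probability is 81 percent that the study will detect a treatment difference at a two-sided 0.05 significance level". Two inputs are given: a between-arm difference of 18.4 units in the week-15 change, and a spread stated as "the standard deviation of the change in SRS score is 22.0".

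The paragraph concludes that 50 participants "will have more than enough power to detect significantly changes in majority of the outcomes listed above". It gives no loss-to-follow-up rate and no inflation for loss. Loss appears only in the preceding Statistical Analysis text, as a missing-at-random assumption for the mixed model.

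The Background (section 4, Preliminary data) describes the earlier trial by the same investigators, in which 44 were randomized: "Forty participants (14 on placebo and 26 on sulforaphane) completed the trial".

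**The concern.** The SRS line contradicts itself. A reader cannot tell whether 44 or 48 children are needed, and the two readings fall on opposite sides of 80% power. In each of the other four lines of the paragraph the arms add up to the total (20 + 20 = 40 once, 22 + 22 = 44 three times), so the fault is confined to this one.

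The choice also affects how much loss the plan can absorb. If 44 is right, 50 enrolled leaves room for six losses. If 48 is right, it leaves room for two. Aim 1 is framed in terms of social responsiveness, which is what the SRS measures, so anyone interpreting the SRS result will look to this line for the trial's sensitivity.

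**Working it through.** **Inputs, all from Power Calculations unless noted.** Difference δ = 18.4; SD σ = 22.0; two-sided α = 0.05; total 48; printed arms 22 and 22; enrolment 50, allocated 1:1. Earlier trial (section 4): 44 randomized, 40 completed.

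**Formula.** For n per arm, the noncentrality is λ = δ / (σ√(2/n)). Power is the probability that a noncentral t variable with 2n − 2 degrees of freedom and noncentrality λ falls outside ± the two-sided 5% critical value. The normal approximation is Φ(λ − 1.96).

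**1. Check the method on a line that is consistent.** The ABC line has 22 + 22 = 44, δ = 19.4, σ = 22.1 and stated power 81%. Here λ = 19.4 / (22.1 × √(2/22)) = 2.91. The t-test gives 81.2% and the normal approximation 82.9%. The t-test is the closer match, so it is used as the main method below.

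**2. Sum of the SRS arms.** 22 + 22 = 44, which is 4 short of the stated 48.

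**3. SRS power by arm size.**

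| Per arm | Total | λ | t-test | Normal approx. |
|---|---|---|---|---|
| 22 | 44 | 2.77 | 77.3% | 79.2% |
| 23 | 46 | 2.84 | 79.2% | 81.0% |
| 24 | 48 | 2.90 | 81.0% | 82.6% |
| 25 | 50 | 2.96 | 82.6% | 84.1% |

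The plan's 81% is reproduced by 24 + 24 = 48. It is not reproduced by the printed arms: 77.3% is 3.7 points below it, and 79.2% by the normal approximation is still under 80%. Arms of 22 and 26 would also total 48 and give 80.7%, but the line prints 22 for both arms and allocation is 1:1. The likeliest explanation is that 22 and 22 were carried over from the lines above.

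**4. Margin for loss.** From 50 to 48: 1 − 48/50 = 4.0%. From 50 to 44: 1 − 44/50 = 12.0%, but power is then 77.3%.

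**5. Illustration with the earlier trial's loss.** Loss was (44 − 40)/44 = 4/44 = 9.1%. Applied to 50 this leaves 50 × 40/44 = 45.5 children.

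| Evaluable | SRS, t-test | SRS, normal approx. | ABC, t-test |
|---|---|---|---|
| 45 | 78.3% | 80.1% | 82.1% |
| 45.5 | 78.7% | 80.5% | 82.5% |

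Against 81.0%, the SRS shortfall by t-test is 81.0 − 78.7 = 2.3 to 81.0 − 78.3 = 2.7 points.

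**The case against.** The best reply is that this is one misprint and nothing in the design depends on it. The total and the power agree with each other at 24 per arm. The line counts patients entering the study, and 50 are to enter, which gives 82.6%. No rule in the plan uses 22 per arm for SRS. That stands as regards consequence. It does not make the printed line correct, and the text alone does not tell a reader which number to trust.

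The loss illustration also has limits. The 9.1% comes from males aged 13–30 treated for 18 weeks, whereas this trial treats children aged 3–12 for 15 weeks in its blinded phase. By the normal approximation, power at that loss is still about 80%. The planned mixed model uses week-7 data from children who leave before week 15, so a completers-only t-test overstates the damage. All of this stands, which is why the figure is offered as an assumption to be stated and not as a forecast.

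A reader might go further and infer that the plan's claim of ample power is refuted. It is not. The closing sentence speaks only of a majority of the outcomes, and SRS is one of five powered outcomes and a secondary one. Only the opening promise of at least 80% is touched.

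A reader might also infer that 18.4 units is optimistic, because in the earlier trial "SRS scores decreased by an average of -15 units in the sulforaphane group compared to -3 units in participants on placebo", a difference of 12. The documents do not support that. Pairing 12 with the new plan's SD of 22.0 mixes two sources. The earlier SD is not reported. If p = 0.02 came from a two-sample t-test on the 26 and 14 completers, the SD would be about 12 / (2.43 × √(1/26 + 1/14)) = 14.9, and the standardized effect 12/14.9 = 0.81, close to the planned 18.4/22.0 = 0.84. The test behind that p-value is not named, so the comparison settles nothing either way. No criticism of the assumed effect is made here.

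**Conclusion.** The SRS line is wrong as printed. Its arms total 44 against a stated 48, and on its own inputs those arms give 77% (t-test) or 79% (normal approximation), not 81%. The total and the power are consistent with 24 per arm, so the arm sizes are most likely the error. That is an inference from the arithmetic, and the sponsor should confirm it.

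Read as 48, the line leaves a 4% margin within 50 enrolled, and the paragraph states no loss rate. With an assumed 9% loss and completers only, SRS power would be about 78–79% and ABC power about 82% by t-test. The SRS effect is 2 to 3 points on a secondary endpoint: worth stating, but not a threat to the trial.

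**What to change.** In section 12, Power Calculations, make one of two corrections to the SRS line: 24 on placebo and 24 on sulforaphane, total 48, 81%; or 22 and 22, total 44, 77%. The first is the more likely intention.

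If the second is chosen, the opening promise of at least 80% for every listed outcome needs an exception for SRS.

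Add one sentence on loss. For example: with an assumed loss of about 9% (4 of 44 in the earlier trial, an older group treated for 18 weeks), about 45 evaluable children would give roughly 78–79% power for SRS and 82% for ABC by two-sided t-test, not counting partial data used by the mixed model.

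The cost is the wording of one paragraph and a slightly less favourable power statement. Enrolment, conduct and analysis do not change.
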